7.3 Study Subjects

7.3.1 *Disposition of Subjects*

Subject disposition will be summarized for all randomized subjects by treatment group and over all subjects combined. Summaries will include the number and percentage of subjects in each analysis population, completing the study, and discontinuing the study early by the primary reason for discontinuation. Subject disposition will also be summarized separately for each study center.

7.3.2 *Protocol Deviations*

Major protocol violations will be summarized by treatment group and over all subjects combined for the Safety Population. Major protocol violations may include, but will not be limited to the following:

- Violation of eligibility criteria;
- Randomization error;
- Non-compliance with study drug dosing;
- On-study administration of a prohibited medication;
- Unauthorized changes to protocol procedure that could potentially affect subject safety or are a flagrant deviation of protocol defined procedures

All major protocol violations will be determined and appropriately categorized prior to database lock and prior to breaking the blind of the treatment group assignments. The number and percentage of subjects with any major protocol violations as well as the number and percentage of subjects with violations within each category will be presented. A per subject listing will be provided for all protocol violations. All protocol violations will be determined and appropriately categorized prior to database lock.

7.4 Efficacy

7.4.1 *Datasets Analyzed*

All efficacy summaries will be based on the mITT Population; select efficacy summaries will also be produced on the PP Population. A data listing of subjects excluded from the mITT or PP Population, to include the reason for exclusion, will be presented.

7.4.2 *Demographic and Other Baseline Characteristics*

Demographic variables including age, sex, ethnicity and race, will be summarized by treatment group and over all subjects combined for the Safety, mITT, and PP Populations.

Age will be summarized using descriptive statistics. Sex, ethnicity, and race will be summarized with the number and percentage of subjects in each parameter category.

Baseline characteristics include medical history, height, weight, time since onset of axillary hyperhidrosis symptoms and body mass index (BMI). BMI will be calculated as: $\text{weight (kg)} / (\text{height (cm)} / 100)^2$. Time since onset of axillary hyperhidrosis symptoms will be reported in months and calculated by dividing the duration in days by $(365.25 / 12)$. Baseline characteristics will be summarized for the Safety Population by treatment group and for all subjects combined. Height, weight, and BMI at baseline will be summarized using descriptive statistics. Medical history events will be coded to system organ class using the Medical Dictionary for Regulatory Activities (MedDRA, version 19.1). Frequency counts and percentages to summarize subjects reporting abnormal medical history by system organ class as will be presented.

7.4.3 *Measurements of Treatment Compliance*

Study drug compliance will be calculated for each subject by taking into account whether a subject took all doses of study drug as instructed through dosing deviations collected on the CRF. Compliance to the study treatment regimen will be determined as the total number of doses received divided by the number of expected doses, multiplied by 100. As study drug is applied 1 time daily per axilla for 42 days, the expected number of doses will be the number of days between the date of last dose of study drug minus the date of first dose of study drug, plus one, times two. The number of doses received will be the number of days between the date of last dose of study drug minus the date of first dose of study drug, plus one, times 2 minus the number of missed doses recorded on the Dosing page of the CRF. Dosing compliance will be summarized using descriptive statistics based on the Safety Population, and separately based on the PP Population.

7.4.4 *Primary Efficacy Endpoint Analysis Methods*

The mean of the items in sections No. 1, 2, and 3 of the HDSM-Ax (11 sub-items in total) will be used for analysis. The mean will be derived by taking the total score and dividing by the number of questions answered. Subjects must answer at least 6 of the 11 sub-items to be evaluable for HDSM-Ax total score. Baseline and End of therapy values are defined as follows.

- Baseline value = average of two screening values, i.e., Visit 1 and Visit 4
- End of therapy value = average of Days 41, 42, and 43 measurements, i.e., Visit 11, Visit 12, and Visit 13, respectively.
- End of Therapy Imputed value = includes subjects missing all end of therapy values, where data is imputed by the last three available post-baseline visits.

7.4.4.1 *Primary Efficacy ANCOVA*

The primary efficacy endpoint is the change from baseline to the end of therapy in the mean HDSM-Ax score. The primary efficacy endpoint will be analyzed both as a continuous measure and as a binary outcome. As a continuous measure, the HDSM-Ax change scores will be compared between treatment groups in pairwise fashion by an ANCOVA model adjusting for the baseline HDSM-Ax score. The analysis will be performed with no imputation of missing data. As a binary measure, i.e. achieving a ≥ 1 -point improvement or not from baseline to end of therapy, a binary logistic regression will be performed with treatment assignment and baseline HDSM-Ax score as independent variables in the model. Any subject without a definable 1-point improvement (e.g., missing data) between Baseline and End of Treatment will be considered a non-responder. P values will generally be regarded as descriptive and statistical significance will be assessed using a gate-keeping hierarchy as described in Section [7.4.6.5](#) for both the continuous measure and binary data analyses.

The null hypothesis to be tested for the continuous measure is as below:

$$H_0: \mu_A \geq \mu_P;$$

where μ_A and μ_P represent the true underlying mean change scores for Treatment A (active drug) and Treatment P (vehicle), respectively. The alternate hypothesis to be tested is that the true active treatment group mean change score is smaller than the true vehicle group mean change score:

$$H_1: \mu_A < \mu_P;$$

Tested in the logit scale, the null hypothesis for the dichotomous outcome is that the true proportion of subjects with a 1 point or more improvement is lower in the active treatment group:

$$H_0: P_A \leq P_P;$$

The alternate hypothesis to be tested is that the true proportion of subjects with a 1 point or more improvement is higher in the active treatment group:

$$H_1: P_A > P_P;$$

7.4.4.2 *Sensitivity Analysis by Mixed Effects Models*

As a method that is known to be robust to missing data, mixed model repeated measures (MMRM) analyses will also be performed for the primary efficacy endpoint using all available HDSM-Ax change from baseline data on study days 8, 15, 22, 29, 36, and end of therapy. As fixed effects, treatment (active treatment group or vehicle gel), baseline HDSM-Ax score and visit (included in the class statement as a class variable) and baseline*visit interactions will be

included in the model both without and with treatment*visit interaction terms. Subject will be analyzed as a random effect. Similarly, MMRMs will also be performed for the primary efficacy endpoint using HDSM-Ax dichotomized response data, and HDSM-Ax + GSP dichotomized response data. The models will be the same as the model for continuous data but the dependent variable of interest will be the response status with a logit link, using the SAS Proc GLIMMIX module. Both the heterogeneous CS (CSH) and TOEP (TOEPH) covariance structures will be considered and the structure with lower AIC will be used. The percentage of responders will also be summarized at each visit in the result table.

MMRM analysis as described above will also be performed for continuous GSP data (both Normal model and using rank transformed data) and binary GSP response (i.e. 50% reduction from baseline) data.

7.4.4.3 *Additional Sensitivity Analysis*

An additional sensitivity analysis will be performed as follows. For subjects missing all 3 end of therapy values, the data will be imputed by the last three available post-baseline (i.e., from Day 8 onward) assessment values. This analysis will be performed for both the continuous data analysis and the binary data analysis using the same ANCOVA models as described above.

7.4.5 *Secondary and Other Efficacy Endpoint Analysis Methods*

Baseline and End of Therapy values for HDSS and GSP are defined as follows.

HDSS:

- Baseline value = average of two screening values, i.e., Visit 1 and Visit 4
- End of Therapy value = average of Days 41, 42, and 43 measurements, i.e., Visit 11, Visit 12, and Visit 13, respectively.
- End of Therapy Imputed value = includes subjects missing all end of therapy values, where data is imputed by the last three available post-baseline visits.

Gravimetric Sweat Production (both axilla combined total):

- Baseline value = the median of GSP1, GSP2, and GSP3 measurements obtained on Visit 2, Visit 3, and Visit 4, respectively. The mean value of the same visits will also be used for analysis.
- End of Therapy value = the median of GSP4, GSP5, and GSP6 measurements obtained on Visit 11, Visit 12, and Visit 13, respectively. The mean value of the same visits will also be used for analysis.

- End of Therapy Imputed value = includes subjects missing all end of therapy values, where data is imputed by the last three available post-baseline visits.
- Where data from a single axilla is missing, data will be imputed by using the median of the last 3 available values for that axilla.
- Analyses of continuous data will be performed using both Normal model and rank-transformed data.

DLQI:

The DLQI total score is calculated by summing answers to questions 1 through 10, including both parts of Question 7. All questions must be answered at the first DLQI assessment. Subsequent DLQI assessments with a single missing answer will be scored 0 for that question and totaled. Subjects with more than one missing question will have the instrument dropped for that visit.

The DLQI's change from baseline at 43 days (Visit 13) will be compared between each BBI-4000 active arm and the vehicle arm using an ANCOVA model adjusting for the baseline DLQI score.

With the exception of DLQI, analysis for secondary and other efficacy endpoints will generally be similar to the HDSM-Ax analysis described in Section [7.4.4.1](#) and Section [7.4.4.3](#). For GSP results analyzed as continuous measures, analyses assuming Normality for the data distribution (i.e., comparing means) will be performed using ANCOVA as described in Section [7.4.4](#). In addition, continuous gravimetric change scores will also be analyzed with rank transformed data using the t test for ANCOVA models. For both Normal model and non-parametric ANCOVA, treatment and baseline value will be the independent variables and continuous gravimetric change scores or rank scores (of change values) will be the dependent variable as appropriate.

All non-primary analyses will be based on available data without missing data imputation unless otherwise specified.

A table by treatment arm and visit summarizing the number of subjects with non-missing data will be also provided for HDSM-Ax, HDSS, and GSP. Subjects with non-missing data will be summarized for Visits 1 and 4, combined, Visit 1, Visit 4, and missing data at both Visit 1 and Visit 4. The number of subjects with non-missing data at each of Visits 6 through Visit 14 will be summarized, and subjects with complete data at Visits 11, 12, and 13, combined, any 2 of the three (Visit 11, 12, or 13), any one of the three, and subjects missing data at all of Visits 11 through 13 will be summarized.

In parallel to the traditional statistical analysis, psychometric evaluation of the HDSM-Ax will be carried out to confirm the most appropriate HDSM-Ax scoring algorithm and to examine internal validity, construct validity (i.e., examinations of the magnitude of correlation between the HDSM-Ax total score (Items 1, 2, and 3) and key variables such as; items 4 and 5 of the HDSM-

Ax, HDSS and gravimetrically measured sweat production), stability, reliability, ability to detect change, and interpretability of clinical trial results. The psychometric evaluation is outside the scope of this SAP and will be described in a separate analysis plan.

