10.3 Efficacy Analyses

Descriptive summaries will be provided for all efficacy endpoints by treatment groups at specified time points. Mean, standard deviation, median, minimum and maximum will be reported for continuous variables. Frequencies and proportions will be reported for categorical variables. For continuous endpoints specified in 10.2, change from baseline will be similarly summarized.

Primary Efficacy Analyses

The mean of the items in sections No. 1, 2, and 3 of the HDSM-Ax (11 sub-items in total) will be used for analysis. The mean will be derived by taking the total score and dividing by the number of questions answered. Subjects must answer at least 6 of the 11 sub-items to be evaluable for HDSM-Ax total score.

Page 47 of 65

Change from baseline to end of therapy for the primary efficacy measure of HDSM-Ax will be analyzed both as a continuous measure and as a binary endpoint. As a continuous measure, the HDSM-Ax change scores will be compared between all active treatment groups and the vehicle group by an ANCOVA model adjusting for the baseline HDSM-Ax score. As a binary measure, i.e. achieving a 1-point improvement or not from baseline to end of therapy, a logistic regression will be performed with treatment assignment and baseline HDSM-Ax score as independent variables in the model. As a phase 2 study, a 1-sided p<0.10 in favor of an active treatment will be regarded as a positive sign for further investigation.

Missing data will not be imputed for the primary analyses. As sensitivity analyses, mixed model repeated measures (MMRM) analyses may be performed using all available HDSM-Ax change from baseline data on study days 8, 15, 22, 29, 36, and end of therapy.

Additional Efficacy Analyses

Analyses for secondary and other efficacy endpoints will be similar to the binary HDSM-Ax analysis described above. For gravimetric results analyzed as continuous measures, analyses assuming Normality for the data distribution (i.e. comparing means) and analyses using rank transformed data (i.e. comparing medians) will both be performed. All non-primary analyses will be based on available data only.

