10.5 Sample Size and Power Estimation

For the binary version of the primary endpoint, i.e. proportion of subjects achieving at least a 1-point improvement in HDSM-Ax from baseline to end of therapy, assume the true response rates

Page 48 of 65

to be 75% for each BBI-4000 arm and 50% for vehicle control (based on prior data). With 100 evaluable subjects at a 1:1 ratio for each pairwise comparison between a BBI-4000 arm and the vehicle arm, i.e. 50 evaluable subjects per arm, the power is approximately 0.87 for observing a response rate difference in favor of BBI-4000 at a 1-sided p<0.10 level. To limit the study-wide false positive rate to 0.10, a gate-keeping hierarchical testing algorithm will be employed. That is, the BBI-4000 15% group will be compared to the vehicle first, if the result is favorable with a 1-sided p<0.10, then the BBI-4000 10% group will be compared to vehicle. Similarly, if the BBI-4000 10 % is favorable with a 1-sided p<0.10, then the BBI-4000 5% group will be compared to vehicle.

For the continuous version of HDSM-Ax change from baseline to end of therapy, assume the true mean difference between each BBI-4000 arm and the vehicle arm to be 0.18, with a common standard deviation of 0.36, i.e. an effect size (mean difference/standard deviation) of 0.50. With 100 evaluable subjects at a 1:1 ratio for each pairwise comparison between a BBI-4000 arm and the vehicle arm, the power is approximately 0.89 for observing a difference in favor of BBI-4000 at a 1-sided p<0.10 level. Same as for the binary version of HDSM-Ax, the gate keeping hierarchical testing algorithm will be employed for the continuous data.

Assuming an approximate 10% non-evaluable rate for the ITT primary efficacy analyses, 220 randomized subjects are targeted for enrollment.

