7.4.6.5 Multiple Comparisons/Multiplicity

To limit the study-wide false positive rate to 0.10, a gate-keeping hierarchical testing algorithm will be employed to assess statistical significance regarding the primary analyses for the primary efficacy endpoint, i.e. ANCOVA analyses on change from baseline in HDSM-Ax score. The hierarchy is, the comparison between BBI-4000 15% group and vehicle group will be considered first, if the result is favorable with a 1-sided $p < 0.10$, then the comparison between BBI-4000 10% group and vehicle will be considered. Similarly, if the BBI-4000 10% group is favorable with a 1-sided $p < 0.10$, then comparison between BBI-4000 5% group and vehicle will be considered. The same gate keeping hierarchical testing algorithm will be employed for both the binary data analysis and the continuous measurement analysis.

The primary efficacy analysis will be performed on the mITT population; the PP population will be utilized for selected efficacy analyses. The PP population is described in Section [7.2](#).

7.4.6.6 *Active-Control Studies Intended to Show Equivalence*

This study does not include an active-control product and is not intended to demonstrate equivalence between any two drug products.

7.4.6.7 *Examination of Subgroups*

There are no planned analyses to assess efficacy results by subgroups.

7.5 **Safety Analysis**

Safety analysis will be carried out for the Safety Population, to include all subjects who receive at least one dose of study drug. Subjects who do not complete the study, for whatever reason, will have all available data up until the time of termination included in the analysis. For safety analysis presented by study visit, the baseline value will be defined as the last value reported prior to first study drug administration.

7.5.1 *Extent of Exposure*

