The study phase of each therapy/procedure will be determined programmatically based on start and end dates. A prior therapy/procedure is defined as any therapy/procedure occurring prior to the date of the first dose of study drug. A concomitant therapy/procedure is defined as any therapy/procedure occurring on or after the date of the first dose of study drug. A therapy/procedure may be defined as both prior and concomitant. If it cannot be determined whether a therapy/procedure occurred prior to the start of study drug dosing due to partial or missing, it will be considered a prior therapy/procedure. Likewise, if it cannot be determined whether a therapy/procedure occurred after the start of study drug dosing, it will be considered concomitant. Therapies and procedures will be reported in a subject listing, and identified as prior or concomitant, and as a therapy or a procedure.

7.6 **Determination of Sample Size**

For the binary version of the primary endpoint, i.e., proportion of subjects achieving at least a 1-point improvement in HDSM-Ax from baseline to end of therapy, the true response rates will be assumed to be 75% for each BBI-4000 arm and 50% for vehicle control (based on prior data). With 100 evaluable subjects at a 1:1 ratio for each pairwise comparison between a BBI-4000 arm and the vehicle arm, i.e., 50 evaluable subjects per arm, the power is approximately 0.87 for observing a response rate difference in favor of BBI-4000 at a 1-sided $p < 0.10$ level.

For the continuous version of HDSM-Ax change from baseline to end of therapy, the true mean difference between each BBI-4000 arm and the vehicle arm will be assumed to be 0.18, with a common standard deviation of 0.36, i.e., an effect size (mean difference/standard deviation) of

0.50. With 100 evaluable subjects at a 1:1 ratio for each pairwise comparison between a BBI-4000 arm and the vehicle arm, the power is approximately 0.89 for observing a difference in favor of BBI-4000 at a 1-sided $p < 0.10$ level.

Assuming an approximate 10% non-evaluable rate for the mITT primary efficacy analyses, 220 randomized subjects are targeted for enrollment.

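### The gated continuous HDSM-Ax analysis is observed-case despite its mITT label, and no planned likelihood estimate at end of therapy checks it

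*SAP*

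**What the plan says.** On the population, SAP 7.4.6.5 says: "The primary efficacy analysis will be performed on the mITT population". SAP 7.2 defines mITT as everyone randomized and dispensed study drug, grouped as randomized.

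On missing data, SAP 7.4.4.1 says of the continuous ANCOVA: "The analysis will be performed with no imputation of missing data". Protocol 10.3 agrees: "Missing data will not be imputed for the primary analyses". Footnote 2 of Table 14.2.1.3 lets any one of the Day 41, 42 and 43 scores supply the end-of-therapy value, so a subject is lost only when all three are absent. The binary version counts a missing result as non-response.

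The loss is anticipated in SAP 7.6: "Assuming an approximate 10% non-evaluable rate for the mITT primary efficacy analyses, 220 randomized subjects are targeted for enrollment". SAP 7.4.5 and Table 14.2.1.1 count, by arm, the subjects with no score at Visits 11 to 13.

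Two sensitivity analyses are planned. SAP 7.4.4.2 fits an MMRM to Days 8, 15, 22, 29, 36 and end of therapy, and credits the method with robustness when data are missing. SAP 7.4.4.3 fills a missing end-of-therapy value from the last three post-baseline scores. In Table 14.2.1.5 the MMRM contributes two p-values per active arm: one for treatment from the model without the interaction, and one for the treatment-by-visit terms jointly. The programming notes say these belong to no particular visit.

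**The concern.** The hypotheses in SAP 7.4.4.1 concern mean change under each treatment, but the ANCOVA estimates a contrast among subjects still providing scores at Days 41-43. The two agree only if, within arm and at a given baseline, those who leave would have responded like those who stay.

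Unequal departure is plausible here. In the earlier 28-day axillary study (Protocol section 1, Study BBI-4000-CL-201), treatment-emergent events were 13.0% on vehicle and 29.2% on 15% gel. The present trial doses for 42 days. Loss of poor responders mainly from vehicle would shrink the estimated effect; loss mainly from an active arm would inflate it.

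The 15% comparison opens the gate for 10% and then 5%, so a shift there carries down the hierarchy. The scores that could correct it are collected, but the planned output does not turn them into an end-of-therapy estimate to set beside the ANCOVA.

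**Working it through.** **Inputs from the documents.** SAP 7.6: "the true mean difference between each BBI-4000 arm and the vehicle arm will be assumed to be 0.18", with a "common standard deviation of 0.36"; 50 evaluable per arm; one-sided 0.10; about 10% non-evaluable of 220 (220 x 0.9 = 198 left). CL-201: 93.7% completed, so 6.3% did not.

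**Inputs assumed.** The documents give no between-visit correlation, no dropout by arm and no dropout mechanism. I use a correlation (rho) of 0.5 to 0.7 between an early change score and the end-of-therapy change, 10% missing, and SD 0.36 at both times.

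**Step 1: the plan's own power.** SE = 0.36 x sqrt(2/50) = 0.072. Power = Phi(0.18/0.072 - 1.2816) = Phi(1.218) = 0.888. Protocol 10.5 says "the power is approximately 0.89 for observing a difference in favor of BBI-4000 at a 1-sided p<0.10 level", so the figure reproduces.

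**Step 2: upper bound for selection in one arm.** If exactly the worst fraction d at the early visit leaves one arm and loss in the other is random, the difference moves by rho x SD x phi(z)/(1 - d).
- d = 0.10: z = 1.2816, phi(z) = 0.1755. With rho 0.5: 0.5 x 0.36 x 0.1755/0.9 = 0.0351, or 19.5% of 0.18. With rho 0.7: 0.0491, or 27.3%.
- d = 0.063 (the CL-201 rate): 13.2% and 18.5%.

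**Step 3: graded selection.** Large-sample simulation, 1,000,000 per arm, true difference 0.18. Early and late changes are bivariate normal, and dropout is logistic in the early change (odds ratio per SD).

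| Dropout pattern | Observed-case difference | Shift |
|---|---|---|
| 10% in each arm, same selection (OR 3) | 0.180 | 0% |
| One common rule on the observed early score (OR 2 to 5) | 0.177 to 0.164 | -2% to -9% |
| 5% active, 15% vehicle, poor responders leave (OR 2 to 3) | 0.168 to 0.157 | -7% to -13% |
| Vehicle only selective (OR 2 to 3) | 0.168 to 0.156 | -6% to -13% |
| Active only selective (OR 2 to 3) | 0.193 to 0.205 | +7% to +14% |
| Opposite selection: poor responders leave vehicle, good responders leave active (OR 2 to 3) | 0.156 to 0.131 | -13% to -27% |

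A likelihood estimate that also uses the early score was run for every row except the common rule. It gave 0.179 to 0.181, within 0.6% of the truth. Carrying the early score forward, a simplified form of SAP 7.4.4.3, gave 0.164 to 0.211. Where selection differs between arms it errs in the opposite direction to the observed-case analysis.

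**Step 4: consequence for the test at 50 per arm.**
- Effect 6% low: 0.1692/0.072 - 1.2816 = 1.068, power 0.86.
- Effect 14% low: 0.1548/0.072 - 1.2816 = 0.868, power 0.81.
- Effect 27% low: 0.1314/0.072 - 1.2816 = 0.543, power 0.71.
- Inflating direction: selection in the active arm alone adds 0.193 - 0.180 = 0.013 to 0.205 - 0.180 = 0.025 whatever the true effect. With no true effect, the chance of passing the 15% step would be Phi(0.013/0.072 - 1.2816) = 0.13 to Phi(0.025/0.072 - 1.2816) = 0.17, against the planned 0.10.

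**The case against.** A reader might infer that the exclusion is hidden. It is not: the rule is in both documents, the 10% loss is built into the sample size, and missingness at Visits 11-13 is tabulated by arm.

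A reader might also infer that the Day 8-36 scores are never used. They enter the MMRM and the last-three-values analysis, and the binary primary keeps these subjects as failures under the same gate. These safeguards are real but limited. The MMRM output has no end-of-therapy contrast, carrying scores forward is not a dependable correction, and the binary result answers a different question from the mean change.

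A third tempting reading is that the effect will move by 10% to 27%. The documents do not support that. Similar dropout in both arms gives 0% to about -9%. The top of the range needs opposite selection in the two arms, or loss of exactly the worst tenth of one arm. CL-201 lost only 6.3%: six withdrawals, five lost to follow-up and one adverse event. Lack of efficacy and worsening condition appear in the disposition table shell, but that is a standard menu and not evidence of mechanism.

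Protocol 7.4 asks subjects who discontinue to complete the Visit 13 evaluations, which include HDSM-Ax. This could shrink the loss. The SAP does not say whether such a score counts as end of therapy, so its benefit cannot be judged.

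Finally, the likelihood method's near-zero bias in step 3 is partly by construction, since dropout there depends only on observed scores, and the estimator was simpler than the SAP model. That stands. Missing-at-random given earlier scores is still a weaker assumption than the one the observed-case ANCOVA needs. This is also a Phase 2 screen at one-sided 0.10 with p-values generally treated as descriptive, which limits the harm.

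**Conclusion.** The point holds in a limited form. The gated continuous analysis is observed-case although labelled mITT, and it is unbiased only if leaving is unrelated to response given arm and baseline. The plan discloses this and includes sensitivity analyses, but none gives a likelihood estimate at end of therapy to check the primary result.

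Neither the size nor the direction of any bias can be fixed from the documents. At 10% missing and an assumed correlation of 0.5 to 0.7, selection confined to one arm shifts the 0.18 difference by 6% to 14% either way. If the effect shrinks, power is about 0.86 to 0.81 in place of 0.89. Equal dropout and selection gives no shift. The case for change rests on a better analysis being already planned at little cost, not on a demonstrated bias.

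**What to change.** Before unblinding:

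1. In SAP 7.4.4.1 and 7.4.6.5, make the gated continuous analysis the active-minus-vehicle contrast at end of therapy from the SAP 7.4.4.2 MMRM with treatment-by-visit and baseline-by-visit terms. Every mITT subject with a baseline and any score from Day 8 on then contributes.
2. Fix the covariance structure in advance, for example unstructured with a stated fallback, in place of the AIC choice between CSH and TOEPH.
3. Keep the observed-case ANCOVA as a sensitivity analysis and describe its set as mITT subjects with an end-of-therapy value.
4. At minimum, if the ANCOVA stays primary, add the MMRM end-of-therapy contrast and its confidence interval beside it in the tables.
5. State how Visit 13 evaluations done at early termination are assigned to visits, in particular whether they can supply the end-of-therapy value.
6. Record the changes in SAP 7.7 and align Protocol 10.3.

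The cost is wording and modest programming; no new data are needed. The model assumes missing-at-random given earlier scores, and subjects with no score from Day 8 on still contribute nothing.
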